#### **4.2.4 Demographics and baseline characteristics**

The baseline demographic characteristics will be summarized by means of descriptive statistics.

The following demographic characteristics will be reported for this study:

- Age (years)
- Sex (Male, Female)
- Race (White, Black or African American, Asian, American Indian or Alaska Native, Native Hawaiian or other Pacific Islander, Other)
- Ethnicity (Hispanic or Latino, Not Hispanic or Latino)

Demographics and baseline characteristics will be show overall, by age group and by start of any newly approved drug for haemophilia (see Section 4.4.4 for the subgroup definition).

#### **4.2.5 Medical or Surgical History and/or Concomitant Diseases**

A disease is considered as medical history if it is not ongoing at baseline visit ("ongoing" box is not ticked).

A disease is considered as concomitant disease if it is ongoing at baseline visit ("ongoing" box is ticked as "Yes").

Medical history and concomitant diseases will be coded using Medical Dictionary for regulatory activities (MedDRA) dictionary and frequency distributions and percentages will be summarized in the Evaluable population by System Organ Class (SOC), and Preferred Term (PT).

Medical history and concomitant diseases will be analyzed separately. Frequency distributions and percentages will be given for both SOC and PT by subject. Subjects experiencing more than one past/concomitant disease event will be counted only once within each SOC and PT.

#### **4.2.6 Prior and concomitant medications**

Medications will be coded using World Health Organization Drug Dictionary (WHO DD).

A medication is considered as prior medication if it is not ongoing at screening visit ("ongoing" box is not ticked).

A medication is considered as concomitant medication if it is ongoing at screening visit (“ongoing” box is ticked as “Yes”).

Prior and concomitant medications will be summarized separately. Frequency distributions and percentages will be summarized in the Evaluable population by Anatomical Main Group (1st level of the Anatomical Therapeutic Chemical (ATC) classification), Chemical Subgroup (4th level of the ATC classification) and Preferred Name.

Subjects taking more than one medication classified in the same category (prior medications or concomitant medications) within the same anatomical main group, chemical subgroup and preferred name will be counted only once.

#### **4.2.7 Other baseline characteristics**

##### History of Physical Activity

The history of Physical Activity will be presented by age group. The following information collected in the eCRF at baseline will be summarized:

- Only for patients that are 12-17 years old:
  - Number and proportion of patients who regularly play activities, entertainment, fun that involve a physical commitment.
  - Number and proportion of patients who practice a sport discipline regularly, albeit at an amateur level, or participate to the school sessions of physical education.
  - Type of sport disciplines.
  - Number and proportion of patients who exercise aerobic activities including low/medium physical intensity (e.g., walking, cycling, swimming) in the context of family, community or school activities.
  - Number and proportion of patients who spend most of the day for the conduct of sedentary activities (e.g., study, videogames, use of electronic devices).
  - Number and proportion of patients who are reluctant to use active means of transport (e.g., walking, cycling or climbing stairs).
- Only for patients that are 18-50 years old:
  - Number and proportion of patients who regularly exercise in their free time, for fun or leisure.
  - Number and proportion of patients who practice a sport discipline or physical exercises planned, albeit on an amateur level.
  - Type of sport disciplines.
  - Number and proportion of patients who exercise aerobic activities also of average physical intensity (e.g., dynamic work, walk to make orders, carry out housework) in the context of daily, family or community.

- Number and proportion of patients who spend most of the day for the conduct of sedentary activities (e.g., working on the PC, driving a vehicle or using electronic devices).
- Number and proportion of patients who are reluctant to use active means of transport (e.g., walking, cycling, or climbing stairs).

### History of Haemophilia

The following information collected in the eCRF at baseline will be summarized:

- Confirmation of Haemophilia A diagnosis (Yes/No).
- Time from diagnosis (years).
- Disease severity (Moderate/Severe Haemophilia).
- History of positive inhibitor against FVIII (Yes/No) and time since the inhibitor was eradicated (years).
- History of known thrombophilia (Yes/No).
- History of anaphylaxis (Yes/No).
- Number of bleeds during 24 weeks prior to baseline (0, 1/2, 3/4, 5/6, >6, Unknown).
- Number of school/work days missed during 24 weeks prior to baseline (for the patient) (0, 1/2, 3/4, 5/6, >6, Unknown).
- Number of days hospitalized during 24 weeks prior to baseline (for the patient) (0, 1/2, 3/4, 5/6, >6, Unknown).
- Number of school/work days missed during 24 weeks prior to baseline (for the caregiver) (0, 1/2, 3/4, 5/6, >6, Unknown).
- Age of possible early retirement (for parent or caregiver).

All parameters related to the history of haemophilia will be shown overall, by age group and by start of any newly approved drug for haemophilia (see Section 4.4.4 for the subgroup definition). Moreover, the disease severity will also be summarized by frequency of physical activity.

## 4.3 EVALUATION OF COMPLIANCE AND EXPOSURE

### 4.3.1 Exposure to use of the fitness tracker

On a per patient basis, the evaluation of the exposure to the use of the fitness tracker will be done using the following formula:

$$\text{Exposure (days)} = \text{date of the last valid day} - \text{date of first valid day} + 1$$

where a “valid day” is defined as a day in which the fitness tracker is worn for at least 10 hours. The wearing time derivation is presented in the Appendix 3.

#### **4.3.2 Compliance to use of the fitness tracker**

On a per patient basis, the evaluation of the compliance during the overall study period will be done using the following formula:

$$\text{Compliance (\%)} = \frac{\text{total number of valid days during the observational period}}{\text{end of study date} - \text{baseline date} + 1} \times 100$$

where a “valid day” is defined as a day in which the fitness tracker is worn for at least 10 hours. The wearing time derivation is presented in the Appendix 3.

Compliance will be summarized by means of summary statistics on the overall sample and by age group.

Compliance to the use of fitness tracker will also be summarize by start of any newly approved drug for haemophilia (see Section 4.4.4 for the subgroup definition).

##### **4.3.2.1 Compliance to use of the fitness tracker (respect to the exposure)**

On a per patient basis, the evaluation of the compliance during the period defined by the exposure will be done using the following formula:

$$\text{Compliance (\%)} = \frac{\text{total number of valid days}}{\text{between the first and last valid days}} \times 100$$

where a “valid day” is defined as a day in which the fitness tracker is worn for at least 10 hours. The wearing time derivation is presented in the Appendix 3.

This definition of compliance will be used to define the Evaluable population.

## **4.4 EFFICACY ANALYSIS**

#### **4.4.1 Co-primary Endpoints**

All the co-primary endpoints presented in Section 2.2.1, i.e.:

- active minutes:
  - heart zone minutes (overall, fat-burn minutes, cardio minutes, peak minutes)
  - active zone minutes (overall, lightly active minutes, fairly active minutes, very active minutes)
  - MVPA minutes
- METs
- number of steps

will be summarized at subject level as median per day (i.e. the median of each parameter will be calculated by using all the valid days collected during the observational period for each subject). Each parameter, derived as median per day at subject level, will be analyzed by means of descriptive statistics as described in Section 4. The 95% confidence interval for the mean will be also displayed.

The statistics will be shown overall and by age groups (12-17, 18-30 and 31-50). The comparison among the age groups will be performed by means of a one-way ANOVA or, if assumptions of normality is not confirmed (by a visual inspection: histogram and qq-plot), by means of a Kruskal-Wallis test.

Daily physical activity will also be summarized:

- by start of any newly approved drug for haemophilia (see Section 4.4.4 for subgroup definition).
- by COVID-19 period on the EVL population (see Section 4.4.4 for subgroup definition).
- by month through the entire observational period on the EVL to observe the impact of COVID-19.

Data will be summarized at subject level considering data collected in each period above-mentioned.

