## **STATISTICAL ANALYSIS PLAN AMENDMENT RATIONALE**

### **Amendment 1.1: 02 February 2022:**

All the co-primary endpoints presented in Section 2.2.1, i.e.:

- active minutes:
  - heart zone minutes (overall, fat-burn minutes, cardio minutes, peak minutes)
  - active zone minutes (overall, lightly active minutes, fairly active minutes, very active minutes)
  - MVPA minutes
- METs
- number of steps

will be summarized at subject level as median per day (i.e. the median of each parameter will be calculated by using all the valid days collected during the observational period). In this way it is possible to obtain a more robust measurement that is not affected by the presence of outliers related to scattered peak of physical activity or errors in the measurement related to the fitness tracker.

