## 2.2 OUTCOME MEASURES

The co-primary outcome measures are given by the physical activity data collected through a wearable device (i.e., fitness tracker) in terms of active minute, METs and steps count.

According to the protocol (see Study protocol, Section 6.1.1), a valid day of monitoring is defined as at least 10 wearing hours per day. Only data from days in which the fitness tracker was worn for at least 10 hours will be included in the statistical analysis (see Appendix 3 for the derivation of the wearing time).

The minutes are saved in two different sets of data collected by the fitness tracker. For each set, minutes are categorized by intensity of the activity done.

The first set is comprised of the minutes categorized accordingly to the time collected in each heart zones (following referred as “heart zone minutes”):

- fat-burn minutes,
- cardio minutes,
- peak minutes.

The second set is comprised of the minutes categorized accordingly to the active zones (following referred as “active zone minutes”):

- lightly active minutes,
- fairly active minutes,
- very active minutes.

The conversion from heart zones to active zones is not shared by the owner of the fitness tracker but it is known that it is based on the METs (Metabolic Equivalent of Task). The MET is the objective measure of the ratio of the rate at which a person expends energy, relative to the mass of that person, while performing some specific physical activity compared to a reference. METs calculated by the fitness tracker are not directly available but must be derived.

In our analysis, the METs will be derived by using the following formula:

$$1 \text{ MET} = \frac{\text{kcal}}{\text{kg} * \text{h}}$$

where:

- $kcal$  will be given by the sum of calories collected by the fitness tracker during the time spent in fat-burn, cardio and peak heart zones, respectively.
- $kg$  will be given by the weight collected in the eCRF at baseline and every 3 months when the observation visit is conducted and the weigh is collected (the weight is assumed constant between each visit and the subsequent, in case of missing assessment, the last available value will be carried forward).
- $h$  is the time that will be derived as sum of fat-burn minutes, cardio minutes, and peak minutes.

The minutes will be also analyzed in terms of overall sum:

$$\begin{aligned} \text{overall heart zone minutes} &= \\ &= \text{fatburn minutes} + \text{cardio minutes} + \text{peak minutes} \end{aligned}$$

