#### **4.1.2 Evaluable population**

The evaluable population will consist of all enrolled patients with at least 6 valid months of physical activity evaluations during the study.

The patients with 6 valid months of physical activity will be defined by the presence of the two following conditions:

- an Extent of Exposure to the fitness tracker of at least 6 months (180 days) (see Section 4.3.1 for the definition of Exposure).

AND

- a compliance to the use of the fitness tracker of at least 50% in the period defined by the extent of exposure (see Section 4.3.2.1 for the definition of the compliance respect to the exposure).

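### The patient-level median per day is exactly 0 for any intensity category absent on more than half of valid days, so within that category it cannot separate occasional or regular exercise from none

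*SAP*

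**What the plan says.** SAP 4.4.1 lists the co-primary parameters: heart-zone minutes (overall, fat-burn, cardio, peak), active-zone minutes (overall, lightly, fairly, very active), MVPA minutes, METs and steps. Each "will be summarized at subject level as median per day", and the same sentence adds that "the median of each parameter will be calculated by using all the valid days collected during the observational period for each subject". The patient medians are then described with a mean and 95% CI, overall and for ages 12-17, 18-30 and 31-50. The age groups are compared by ANOVA or Kruskal-Wallis.

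Under SAP 2.2, "a valid day of monitoring is defined as at least 10 wearing hours per day"; no activity is required. The Evaluable population (SAP 4.1.2) needs at least 180 days of exposure and "a compliance to the use of the fitness tracker of at least 50% in the period defined by the extent of exposure".

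Amendment 1.1 gives the reason for the median: a more robust measure, "not affected by the presence of outliers related to scattered peak of physical activity", or by tracker measurement errors.

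Protocol 6.7.1 plans descriptive statistics of the daily values, for example weekly or monthly, and prescribes no within-patient median.

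**The concern.** A median suits a quantity that is present on nearly every day, such as steps. Minutes in a higher-intensity category may be intermittent: several on training days and none otherwise. For such a category the median records only whether the patient was active on more or fewer than half of the days. It loses how much was done.

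The primary objective is to document how much activity patients do, by age. For an intermittent category the planned row could show 0 both for a patient who trains three times a week and for one who never does. The age-group means, intervals and tests would inherit that loss. Exercise on a minority of days is also part of what the study sets out to measure, so protection against scattered peaks has a cost here that the amendment does not discuss.

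**Working it through.** **The plan's own figures.** The documents give no figure for the behaviour of the median. The only figure attached to the primary means is the precision statement in SAP 2.3 and 2.3.1, and it reproduces. At n = 150 a half-width of at most 0.17 SD has probability 0.831. At n = 107 the half-width reached with 80% probability is 0.202 SD. This does not bear on the point.

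**Inputs from the SAP.** The median is taken over all valid days (4.4.1). A valid day is 10 wear hours (2.2). The fewest valid days for an evaluable patient is 180 x 0.50 = 90 (4.1.2).

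**Assumptions, not in the documents.** A valid day without minutes in a category is stored as 0. Sessions last 45 minutes, fall on different days, and are the patient's only minutes in that category.

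**Step 1: fixed weekly pattern.** With k sessions a week, the mean per day is 45k/7. The median is 0 if k < 3.5 and 45 otherwise.

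| k per week | true min/week | mean min/day | median min/day |
|---|---|---|---|
| 0 | 0 | 0 | 0 |
| 1 | 45 | 6.4 | 0 |
| 2 | 90 | 12.9 | 0 |
| 3 | 135 | 19.3 | 0 |
| 4 | 180 | 25.7 | 45 |
| 7 | 315 | 45.0 | 45 |

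Session length does not affect where the zeros fall. At k = 4 the median is 45/25.7 = 1.75 times the mean.

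**Step 2: active days falling at random.** Let X be the number of non-zero days among n, binomial with probability p. The median is 0 when X < n/2.

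| p | n = 90 | n = 180 | n = 365 |
|---|---|---|---|
| 2/7 | about 1.000 | about 1.000 | about 1.000 |
| 3/7 | 0.896 | 0.968 | 0.997 |
| 4/7 | 0.071 | 0.022 | 0.003 |

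**Step 3: consequence for an age-group test (illustration only).** Take 107 patients in assumed groups of 27, 40 and 40, with 250 valid days each. The groups average 1, 2 and 2 active days a week, with about 60 minutes on an active day. Over 99.9% of patient medians were 0. Kruskal-Wallis rejected in 0% of 300 simulated runs on the medians and in 100% on the patient means. The pattern was chosen to show the mechanism and is not a forecast for this study.

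**Step 4: contrast with steps.** Assume rest days averaging 6000 steps and exercise days 12000, each with SD 2000. Three exercise days a week raise the median from about 6000 to about 8100, so the median still separates these patients.

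**Step 5: link to WHO adherence.** SAP 2.2.1 takes the adherence measures from its Section 4.1, which defines the analysis populations. If 4.4.1 is meant, consider an adult with 3 x 50 = 150 fairly active minutes a week and no other such minutes. This adult meets the 150-minute threshold on accumulated minutes, but 7 x a median of 0 = 0 would class the patient as sedentary.

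**The case against.** The strongest reply has four parts.

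- **Robustness has a real basis.** Amendment 1.1 names tracker errors as well as scattered peaks. The ITT population (SAP 4.1.3) has no minimum number of valid days, and one artefact day can dominate a mean taken over few days. This stands, and is why the median should stay.
- **Frequency is partly covered elsewhere.** SAP 4.4.2 plans a weekly rate and the minutes per single activity for each activity type, by age group. For activities that the tracker records, this separates 0 from 1, 2 or 3 sessions a week. It is a secondary analysis by type, however, and gives no total minutes by intensity per day or week. It narrows the gap without closing it.
- **No daily distributions are available.** A reader might infer that the primary tables will be mostly zeros. The documents do not show that. SAP 4.4.2 uses a pre-bleed MVPA median above 0 as a cut-off, so zero values are contemplated, but their frequency is not given.
- **The study is descriptive.** The tests are exploratory and unadjusted, and the documents tie no decision rule to these rows. This bears on severity, not on whether the rows answer the primary objective.

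**Conclusion.** The point holds for intermittent categories and should be fixed. Where a category is empty on more than half of valid days, the patient median is exactly 0, and 1 to 3 sessions a week cannot be told from none. At 4 sessions a week the median overstates the daily average (45 against 25.7 min/day with 45-minute sessions). The zero result follows from the SAP's definition, provided that empty days are stored as 0. The sizes rest on the assumed session pattern. Peak, cardio and very active minutes are plausibly affected, and fairly active or MVPA minutes possibly.

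Three stronger readings are not supported:

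- That regular exercisers look like inactive patients across the whole co-primary set. Steps, lightly active and overall active minutes are much less affected.
- That the WHO classification is certainly affected, or certainly not. The cross-reference leaves this open.
- That component rows which do not sum to the MVPA or overall row contradict each other. Medians need not add up.

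**What to change.** 1. In SAP 4.4.1, for the heart-zone, active-zone and MVPA minutes, add at patient level the mean per valid day (x 7 for minutes per week) and the percentage of valid days with more than 0 minutes. Show both by age group.
2. Run the planned age-group comparison on the patient means as well as on the medians.
3. Keep the median per day as planned, for its robustness to tracker errors.
4. Correct the cross-reference in SAP 2.2.1 and base WHO adherence for adults on accumulated weekly minutes. For ages 12-17, where the criterion is minutes per day, state how the daily values are combined.

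The cost is SAP wording and extra table rows from data already held. The downside is that means are more sensitive to artefact days, especially in ITT patients with few valid days. Showing mean and median side by side lets the reader see where they diverge.

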## **4. STATISTICAL METHODS**

Appropriate descriptive statistics will be produced, according to the variable. For continuous data n, mean, standard deviation (SD), median, I and III quartile, and range (minimum and maximum) will be presented. For categorical data, frequency distributions and percentages will be presented.

Unless otherwise specified, hypothesis testing (exploratory in nature) will be carried out at the alpha = 0.050 level (two-sided). For all inferential analyses, the p-values will be rounded to three decimal places. Due to the exploratory nature of this study, no adjustment for multiplicity will be made.

Any unplanned analyses as well as deviations from the original SAP will be clearly documented in the Clinical Study Report.

All the data collected and derived in the study will be presented in subject data listings.

With reference to the ePROs and physical activity data (i.e. all data derived from ePRO app and the fitness tracker), only data collected between the informed consent date and Date of patient completion or withdrawal (extremes included) will be analyzed. For the interim analysis, the minimum between Date of patient completion or withdrawal and the cut-off date will be considered as upper bound.

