#### **4.4.2 Secondary and Exploratory Endpoints**

The endpoints assessed via the ePRO application that require to be evaluated at specific timepoint need to be “remapped” at each time point by deriving from the date the corresponding week/month starting from the baseline date. In case that more than one observation occurs within the same week/month, the mean among the two observations will be used.

**To document physical activity, particularly in terms of active minutes, by ages categories (12-17, 18-30 and 31-50 years), by type of physical activity and by intensity (as per fitness tracker default categorization)**

Data will be analyzed as for the primary endpoint described in Section 4.4.1 but they will be analyzed at activity level (instead of a daily level).

For example, if we consider “Bike”, the active minutes and METs will be derived as median of the active minutes (heart zone minutes, active zone minutes and MVPA minutes) for single activity (i.e. if Bike is reported twice, the active minutes for Bike will be derived as median of the values reported for each of two activities done).

Moreover, the activity rate will be derived as follow (in the example for “Bike”):

$$\text{Bike weekly rate} = \frac{\text{number of times that Bike is reported on the fitness tracker}}{\text{end of study date} - \text{baseline date} + 1} \times 7$$

For each type of activity, the statistics will be shown overall and by age groups (12-17, 18-30 and 31-50). The comparison among the age groups will be performed by means of a one-way ANOVA or, if assumptions of normality is not confirmed (by a visual inspection: histogram and qq-plot), by means of a Kruskal-Wallis test.

Daily physical activity will also be summarized:

- by start of any newly approved drug for haemophilia (see Section 4.4.4 for subgroup definition).
- by COVID-19 period on the EVL population (see Section 4.4.4 for subgroup definition).
- by month through the entire observational period on the EVL to observe the impact of COVID-19.

Data will be summarized at activity level considering data collected in each period above-mentioned.

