### **To evaluate sleep duration and sleep stages in participant patients.**

The analysis of sleep duration (overall and by stage) will be done as for the primary endpoints described in Section 4.4.1.

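### The age-group ANOVA on the co-primary activity endpoints assumes a common variance that the SAP neither checks nor assures; Welch's ANOVA in that branch is a cheap improvement.

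*SAP*

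**What the plan says.** SAP section 4.4.1 reduces each patient to one value per parameter, the median over that patient's valid days. It summarises these values overall and for ages 12-17, 18-30 and 31-50. Beside the descriptive statistics, "The 95% confidence interval for the mean will be also displayed".

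The test rule follows: "The comparison among the age groups will be performed by means of a one-way ANOVA or, if assumptions of normality is not confirmed", on a look at the histogram and qq-plot, Kruskal-Wallis. The rule covers 11 parameters: four heart-zone, four active-zone, MVPA, METs and steps.

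Section 4.4.2 repeats the rule for each type of activity. It also carries it to sleep: "The analysis of sleep duration (overall and by stage) will be done as for the primary endpoints described in Section 4.4.1".

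Section 4 sets the level: "hypothesis testing (exploratory in nature) will be carried out at the alpha = 0.050 level (two-sided". It adds: "Due to the exploratory nature of this study, no adjustment for multiplicity will be made". Neither document mentions equality of variance, a check of it or an unequal-variance test. SAP section 4.4.3 lists no sensitivity analysis.

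**The concern.** The one-way F-test takes its reference distribution from normal groups with one common variance. The plan looks at the first condition and is silent on the second. If the groups differ in both size and spread, the pooled error term is wrong for the comparison. The test is then liberal when the smaller group is the more variable, and conservative when the larger group is.

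Unequal sizes are plausible, because the bands cover 6, 13 and 20 years of age. Equal spread between adolescents and adults up to 50 is not assured.

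The fallback raises a different issue. The null of Kruskal-Wallis is that the three distributions are identical. With skewed data it can reject when the three means printed beside it, with their CIs, are the same.

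At stake is how a p-value is read. Activity by age category is the primary objective, and this is its only planned test. A small p-value could reflect a difference in variability, or a real difference in means could be missed.

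**Working it through.** **Inputs from the documents.** N = 107 (SAP 2.3.1); three age groups; two-sided 5% level; no multiplicity adjustment; no age-group sizes or SDs.

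**Assumed inputs.** Group sizes in proportion to band width: 107 × 6/39 = 16.5, 107 × 13/39 = 35.7 and 107 × 20/39 = 54.9, taken as 16/36/55. Near-equal sizes of 36/36/35 serve as a contrast. SD ratios run from 1 to 2.

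**The plan's own figures.** The stated precision in SAP 2.3 is for a single overall mean: t/√n × √(χ² at 80%/(n−1)) gives 16.9% of the SD at n = 150, against 17% stated. At n = 107 it gives 20.0% (z) to 20.2% (t), against 20% stated. It does not bear on the age-group test. The figure that does is the 5% level, and it is reproduced when SDs are equal (first row of the table).

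**Direction, by formula.** With equal means, the two mean squares have expectations

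- between: Σ(1 − nᵢ/N)σᵢ² / (k − 1)
- within: Σ(nᵢ − 1)σᵢ² / (N − k)

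The F-test needs their ratio to be 1. For 16/36/55 with the 12-17 SD doubled:

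- between = (0.850 × 4 + 0.664 + 0.486)/2 = 2.276
- within = (15 × 4 + 35 + 54)/104 = 1.433
- ratio = 1.59

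**Rejection rates.** Simulation with normal data, equal means, nominal 5%, 20,000 trials per row (standard error about 0.15 points at 5%):

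| Sizes | SDs | Ratio | F-test | Welch |
|---|---|---|---|---|
| 16/36/55 | 1:1:1 | 1.00 | 4.8% | 4.8% |
| 16/36/55 | 1.5:1:1 | 1.30 | 10.2% | 5.2% |
| 16/36/55 | 2:1:1 | 1.59 | 15.4% | 4.8% |
| 16/36/55 | 1:1:2 | 0.68 | 1.9% | 5.2% |
| 36/36/35 | 1.5:1:1 | 1.00 | 5.3% | 5.0% |
| 36/36/35 | 2:1:1 | 0.99 | 5.7% | 4.7% |
| 36/36/35 | 1:1:2 | 1.01 | 6.4% | 5.0% |

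A wider grid of near-equal sizes, with SD ratios up to 3, put the F-test at 4.8% to 7.0%.

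**Kruskal-Wallis with skewed data.** Lognormal data, 16/36/55:

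- Equal means, CVs 0.5/0.8/1.2: rejects 25.6%. CVs reversed: 32.8%.
- In these cases the medians, mean/√(1 + CV²), are 0.89, 0.78 and 0.64 of the common mean, so the test's own null is false.
- Equal medians, same CVs: 2.9% and 8.5%.

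**Limits of Welch.** Under the same skew with equal means, Welch rejects 5.3%, and 11.8% when the smallest group has CV 1.2. It cannot be computed if a group has zero variance. If only 10% of patients had a non-zero value (assumed), the chance that some group is all zero is 1 − (1 − 0.9¹⁶)(1 − 0.9³⁶)(1 − 0.9⁵⁵) = 1 − 0.815 × 0.977 × 0.997 = 21%.

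**Power cost.** With equal SDs and a 0.7-SD shift in the group of 16, the F-test has 61.5% power and Welch about 59%.

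**The case against.** The strongest reply is that little depends on this test. The protocol's objective is to document activity, its analysis is descriptive with CIs, and formal hypothesis testing is disclaimed. The SAP calls its tests exploratory. Group means, SDs, quartiles and CIs will all be shown, so unequal spread will be visible. This stands, and it limits the point to a cheap improvement.

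Second, every rate above rests on assumed sizes and SDs. This also stands. The rates describe each test on its own, not the two-step rule with its visual check.

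Third, Kruskal-Wallis is a reasonable choice for skewed subject-level medians, and Welch is not safe everywhere. Peak or very active minutes, as daily medians, may be zero for many patients. This stands too, and it argues against using Welch for every parameter.

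A reader might infer that the planned tests reject at several times 5% under a true null. The documents do not support that. They give no sizes or SDs, the direction depends on which group is more variable, and near-equal sizes leave little excess. The largest Kruskal-Wallis rates arise where medians differ, so they are not type I error of that test.

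The objection does not answer the narrow point. The ANOVA branch relies on a condition that the plan never addresses, and a standard alternative avoids relying on it.

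**Conclusion.** The point holds as a cheap improvement. The plan selects the test on visual normality alone, and its ANOVA branch assumes a common variance that is neither checked nor assured. Under the assumed 16/36/55 split with normal data, the actual level is about 10% to 15% if the 12-17 SD is 1.5 to 2 times the others, and about 2% if the 31-50 SD is doubled. With near-equal sizes it is about 5% to 7%. Welch's ANOVA holds near 5% throughout.

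The Kruskal-Wallis branch is not in error. Its hypothesis differs from the displayed means, and the report should say so. No descriptive primary estimate is affected.

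**What to change.** In SAP section 4.4.1, and so in the by-type and sleep analyses of section 4.4.2:

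- Where one-way ANOVA is used, make it Welch's one-way ANOVA.
- Add pairwise differences in mean between age groups with unequal-variance 95% CIs, wherever the group variances are non-zero.
- Keep Kruskal-Wallis for clearly non-normal or zero-heavy parameters, and label it a comparison of distributions, not of the displayed means.

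The cost is a short text change and a standard SAS option (the WELCH option on the MEANS statement of PROC GLM). If the variances are in fact equal, about 2 to 3 points of power are lost. Some excess rejection remains if Welch is applied to strongly skewed data, which is why the Kruskal-Wallis branch should stay.
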